Breathing Counts
NCT03065205
Protocol version date 12.18.17

COMIRB Protocol

COLORADO MULTIPLE INSTITUTIONAL REVIEW BOARD
[name] [contact] [contact]

Protocol #: 16-1845

Project Title: Breathing Counts

Principal Investigator: [name]

Version Date: 12-18-17

I. Hypotheses and Specific Aims:

Adherence to asthma medications has been associated with good asthma control in children¹, however adherence to asthma medications is poor.² Children who are hospitalized due to their asthma are at a significantly high risk of re-hospitalization³, and represent a particularly high risk group. Successful control of asthma in a high-risk population requires a network of care providers who communicate relevant up-to-date information and support asthma control. Additionally, lay health worker interventions have been shown in some cases to decrease missed school days and parental work days.⁴ We propose to evaluate the efficacy of an asthma navigator program in a high-risk population of patients at Children's Hospital Colorado. We will evaluate the ability of the program to improve health outcomes of children who have asthma and who are at high-risk of re-hospitalization. The project will also evaluate the ability of the navigator program to increase the number of stakeholder communications amongst school nurses, program navigators, physicians, caregivers and children.

Specific Aim 1: Evaluate whether or not the addition of an asthma navigator to the current clinical standard of care will lead to sustainably increased levels of adherence compared to historical rates.

Hypothesis: By providing up to date adherence rates to the patient's medical care team and by addressing patient identified barriers, we hypothesize that the addition of an asthma navigator to the standard of care at Children's Hospital will increase asthma medication adherence rates, and that these adherence rates will be sustained over the 3-6 month monitoring period.

Specific Aim 2 Evaluate whether or not the addition of an asthma navigator results in increased levels of communication between PCPs, specialty providers and school nurses.

Hypothesis: The addition of an asthma navigator will result in increased emails and general communication between various providers in a patient's care team.

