	Outcome Measure	Visit 1 (admission visit)	Visit 2 (2 months)	Visit 3 (4 months or end of study)	Visit 4 (6 months or end of
--	-----------------	---------------------------------	-----------------------	--	-----------------------------------

					study)
Aim 1	Adherence (continually monitored during trial)		X	X	X
Aim 2	Communication among providers	X			X
Aim 3	Asthma Related Health outcomes	X	X	X	X

- a. Adherence- measured on adherence monitoring devices. The rate of daily prescribed controller medication use will be monitored. For example, if an individual is prescribed two doses per day and the monitoring device records one doses, then the daily adherence measure will be 1/2 or 50%. The outcome measure will be continuously gathered via the Propeller Health monitoring device ® (Madison, WI). Rate of monthly adherence will be calculated between study visits,
- b. Communication between providers. Communication between providers will be measured in a number of ways. Providers include nurses, parents, physicians and patients. In order to measure any change in communication the following communication metrics will be monitored.
 - i. Number of emails sent between providers will be assessed if email is used as the primary means of communication.
 - ii. A subset of provider teams will possibly be enrolled in asynchronous communication monitoring. This is a method of HIPAA compliant messaging, which involves providers utilizing an application or website, and communicating securely within that platform. We plan to utilize the Stich platform, which is marketed as HIPAA compliant (<https://www.teamstitch.com>). We are currently on a waiting list to possibly test the technology.
 - iii. Providers will be surveyed before and after the intervention to determine if they felt that the navigators adequately improved communication regarding specific patient related issues.
- c. Other asthma related outcomes including asthma control test, symptom assessments, asthma related readmissions or revisits, missed school days, and provider satisfaction.
 - i. Asthma Control Test, a self (or in the case of this study, phone administered)-administered questionnaire with 5 questions which summarizes asthma control, will be used to record asthma control in children 12 or older.
 - ii. Childhood Asthma Control Test (or in the case of this study, phone administered), a parent and child administered questionnaire, will be used to record asthma control for children 6-11 years of age.

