Demographic information including age, sex, race, and other baseline clinical information upon recruitment including duration of asthma, C-ACT score, ACT score, asthma symptoms, lung function, prescribed medication, and asthma related health care use in the previous year will be obtained at enrollment. The distributions of outcomes will be examined for normality using the Anderson-Darling Test. Dependent upon the distribution we will use the Wilcoxon rank-sum test, Mann-Whitney U test or paired T-test to test for significant changes in outcomes during the study period. Longitudinal patterns of adherence will be examined graphically.

Monthly rates of adherence, asthma symptoms, asthma control scores and monthly missed number of school days and number of hospitalizations will be calculated by study arm. Survey information from patients, caregivers, physicians and navigators on the navigator intervention will be reviewed by study staff and summarized qualitatively. Number of rehospitalizations will be obtained via chart review at 1 month, 6 months and 12 months post hospitalization.

The cost-effectiveness of the navigator intervention will be summarized based on medical resource utilization (direct) and loss of productivity (indirect). Medical resources utilization will include medical care resource utilization, asthma medication variables, navigator time and salary, while loss of productivity will be measured using the number of hours caretaker missed work due to participant's asthma, number of hours dependent participant missed school due to his/her asthma, and number of hours independent participant missed work due to his/her asthma. Unit costs will be applied to healthcare resources and loss of productivity and summed to obtain total costs for each subject. Average costs for the study group will be presented.

Power and Sample Size

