The study is limited by time frame and funding for a one year recruitment period. The primary goal of the study is to provide preliminary information on the effect of a navigator program on the patient and caregiver response to asthma disease control. As a pilot and feasibility study, investigators have chosen to enroll a total of 100 patients and up to 400 providers. Through past clinical experience, we know that some months of the year are higher risk for asthma exacerbations, so we expect to screen more patients during the fall and winter than summer or spring. Considering the variable clinical case load Investigators plan on enrolling an average of 10 participants per month. Anticipating an enrollment rate of approximately 20% (in 2015, there were >600 asthma related admissions at Children's Hospital Colorado), investigators state they should be able to enroll up to 100 patients within one year. We plan to enroll up to 4 providers per patient with a simple pre-post survey as well.

The primary hypothesis of interest is to test whether change in adherence rates are different from zero. The smallest detectable difference was based on a paired sample t-test between pre and post adherence scores with a Type I error rate of 0.05 and 90% power. Based on previous studies⁸, investigators assumed a mean adherence rate of 50% with a standard deviation of 22%.

Table X:	
N	Δ
100	8%
65	10%
30	15%

Table X lists the smallest detectable difference (Δ) for by sample size. For the primary aim investigators will be able to detect a change of 8% or more in percent adherence during the study period with the available 100 patients.

F. Summarize Knowledge to be Gained:

- a. **Utility of an asthma navigator in addition to electronic adherence monitoring in improving adherence to asthma medications**
- b. **Utility of an asthma navigator in improving communication amongst all of a patient's medical providers**
- c. **Utility of an asthma navigator in improving other asthma control related outcomes.**

Asthma Control Classification

Control is computed based on taking the entry with the worst outcome in the following age-based tables:

Asthma Control Classification (Age 5-10)

(Age 5-11)	Asthma	Control	Classification
	Well controlled	Not well controlled	Very poorly controlled
Symptoms (manually entered)	≤ 2 days/week but not more than once on each day	> 2 days/week or multiple times on ≤ 2 days/week	Every day in previous week

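### Aim 1 claims sustained adherence, but the plan has only raw monthly rates, a graph and a test with undefined pre and post, so selective loss can distort the time course

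*Combined protocol and SAP*

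**What the plan says.** Section I, Specific Aim 1, hypothesises that adherence will rise and that "these adherence rates will be sustained over the 3-6 month monitoring period".

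Section IV.A takes adherence continuously from the sensors: "Rate of monthly adherence will be calculated between study visits". Table 1 marks no adherence at Visit 1. It labels Visits 3 and 4 as month 4 or month 6, or alternatively the end of study. Section IV.C follows each child for 3 to 6 months, with a different contact schedule for shorter follow-up.

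The Data Analysis Plan calculates monthly rates and adds: "Longitudinal patterns of adherence will be examined graphically". For testing it names the Wilcoxon rank-sum test, the Mann-Whitney U test or a "paired T-test to test for significant changes in outcomes during the study period". Power and Sample Size states the primary hypothesis as "test whether change in adherence rates are different from zero" and continues: "The smallest detectable difference was based on a paired sample t-test between pre and post adherence scores". All 100 enrolled children are counted as available.

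No section gives a repeated-measures model, an analysis set, a missing-data rule, a drop-out allowance or a sensitivity analysis, and none says which months are *pre* and *post*.

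**The concern.** A claim that adherence is sustained concerns how the same children change. A raw monthly mean describes whoever is still contributing that month. The two agree only if those who stop resemble those who stay. Non-adherence is the problem under study, and section II expects adherence to worsen over time even with monitoring, so that resemblance cannot be assumed. There is no control group in which the same loss might cancel.

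The pre/post test has a related weakness. If *post* is a fixed late month, children without it drop out of the test and their recorded months go unused. If *post* is each child's last recorded month, all children with data count, but a 3-month change is pooled with a 6-month change.

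The two rank tests named are one unpaired test under two names. If normality fails, that test would compare all early values with the remaining late ones, with the same change in composition as the curve.

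**Working it through.** **1. The plan's own figure.** The inputs, from Power and Sample Size, are "Type I error rate of 0.05 and 90% power" and "mean adherence rate of 50% with a standard deviation of 22" percent. I read the test as two-sided, because the hypothesis is a difference from zero.

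- Formula: detectable change ≈ (1.960 + 1.282) × SD of change / √n.
- With an SD of change of 22 and n = 100: 3.242 × 22 / 10 = 7.13. The noncentral t gives 7.20.
- For n = 65 and n = 30 the noncentral t gives 8.98 and 13.47. Table X prints 8, 10 and 15.
- An SD of change of 24.5 reproduces the table (8.02, 10.00, 15.00). It corresponds to a pre/post correlation of 0.38: 22 × √(2 × (1 − 0.38)) = 24.5. So does 95% power with SD 22. The plan states neither.
- With 80 complete pairs the detectable change becomes 8.07 (SD 22) or 8.99 (SD 24.5).

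**2. Data left out by a fixed-month test.** Suppose 20 of 100 children leave, spread evenly over months 2 to 6, so that each has 3 recorded months on average. They supply 20 × 3 = 60 of 80 × 6 + 60 = 540 child-months, or 11%. At 35% loss the simulation below gives about 20%. The monthly rates and the graph keep these months.

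**3. Bias.** The documents give no loss rate, correlation or reason for leaving, so these are assumptions:

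- 100,000 children per setting, six monthly values, first-month mean 50, SD about 22;
- within-child correlation 0.4 or 0.6, with child slopes of SD 1.5 points a month;
- true change from month 1 to month 6 of 0 or −10;
- 20% or 35% lost by month 6;
- log-odds of leaving rising by 1 for each 22 points lower adherence (for the slope row, each 1.5 points a month).

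The table gives bias in points; plus means more sustained than the truth. Correlation is 0.4, true change is 0, and each cell shows 20% / 35% loss. A re-run with fresh random numbers differed by at most about 0.3.

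| Leaving depends on | Raw monthly means | Paired, month 6 | Last recorded month | Model, all months |
|---|---|---|---|---|
| Nothing (random) | 0.0 / −0.1 | +0.1 / −0.2 | +0.1 / −0.1 | +0.1 / −0.1 |
| First month | +1.8 / +2.9 | −2.4 / −4.5 | −0.5 / −1.1 | +0.1 / −0.1 |
| Previous month | +2.0 / +3.5 | −0.3 / −0.7 | −2.4 / −3.8 | 0.0 / −0.1 |
| Stable level of the child | +1.8 / +3.3 | 0.0 / 0.0 | −0.1 / 0.0 | +0.7 / +1.3 |
| Current, unrecorded month | +2.8 / +4.6 | +1.0 / +1.4 | +0.8 / +1.1 | +1.6 / +2.6 |
| Child's slope | +1.3 / +2.5 | +1.3 / +2.5 | +0.7 / +1.2 | +1.1 / +2.1 |

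**4. Range over all settings** (both correlations, both true changes).

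- Raw monthly means: +1.3 to +6.0 under every adherence-related mechanism.
- Paired change at month 6: −4.5 to +2.5.
- Last recorded month: with a true change of −10 and purely random early end, it shows −7.7 to −8.8.
- Model: within about 0.15 when leaving is random or depends on recorded adherence; +0.5 to +2.7 when it depends on the unrecorded month, the stable level or the slope.

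**5. Stronger assumptions.** A separate simulation with 27% to 42% loss gave about +3 to +12 for the raw month-6 mean and about −4.4 to +7.5 for the paired change. The model kept +2.9 to +7.5 when leaving depended on the unrecorded current month.

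**The case against.** Three stronger readings are tempting, and the documents do not support them.

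- *The plan analyses only complete cases.* No section says so. The end-of-study labels in Table 1 allow *post* to be each child's last recorded period, and then nobody with early and later data is dropped. What the text shows is an undefined *post*.
- *The paired test drifts towards sustained.* Each child is his or her own control, so the direction depends on why children leave. In several rows the bias is zero or negative.
- *A mixed model removes the bias.* It does so only for loss driven by recorded adherence. In the stable-level and current-month rows it is more biased than the paired test.

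Other points have weight. Monitoring is by sensor, and under the daily scoring rule a monitored child who takes nothing would logically score 0% and not vanish. The team contacts families whose devices do not sync and offers a hub. The 3-to-6-month variation is not tied to adherence. Read literally with SD 22, 82 pairs detect 8 points, so the sample size already tolerates about 18% loss. The study is a single-group pilot and admits its limits.

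These points lower the likely size of the problem. They do not supply an analysis for the time-course claim. The syncing measures concern collection, and the protocol still names a primary hypothesis with a powered test.

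**Conclusion.** The concern holds in a limited form. A hypothesis about sustained adherence is paired with raw monthly rates, a graph and a test whose two time points are undefined, under unequal follow-up and with no rule for loss. If less adherent children stop contributing, the raw curve overstates how well adherence is sustained, by about 1 to 6 points at 20% to 35% loss and more under stronger mechanisms. If loss is random, the curve is essentially unbiased. The pre/post change may err in either direction, depending on the reason for leaving and on whether *post* is a fixed or a last recorded month.

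Every size here rests on assumed loss, correlation and mechanism. The loss of precision is secondary. I would class this as a cheap improvement: it uses monthly data already collected and does not show that the planned result will be wrong.

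**What to change.** 1. Define the *pre* and *post* months.
2. Make the primary adherence analysis a repeated-measures mixed model on all monitored child-months. Use month as a categorical effect, with an unstructured covariance or a random intercept and slope, and name one contrast for the change.
3. Plot the model-based monthly means with 95% intervals and print the number of children contributing under each month.
4. Record each child's planned end date at enrolment, so that planned early end is separated from loss.
5. Keep the paired test as a sensitivity analysis.
6. Add one sensitivity run that sets the missing later months lower than the model predicts, for example by 10 points.

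The cost is SAP wording, one extra field at enrolment and some analysis time, with no new patients or visits. The downside should be stated in the SAP: when leaving depends on unrecorded adherence, the model can be as biased as the paired test or more so. Item 6 is therefore a necessary part of the change.
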